2. OBJECTIVES AND ENDPOINTS

The objectives and endpoints of the study are presented in [Table 2](#).

Table 2: Objectives and Endpoints

Objectives	Endpoints
Primary: 
to evaluate the safety and tolerability of single and multiple ascending oral doses of AQ280, and to determine a safe therapeutic range of AQ280 in healthy subjects	
number of TEAEs per subjectclinically significant abnormalities in vital signs (systolic and diastolic blood pressure, pulse rate, and oral body temperature)abnormal ECG (QTcF interval of >450 msec for males and >470 msec for females, or change from baseline of >30 msec) measured from Day 1 (postdose) up until 48 hours postdose in Part A and up to the follow-up visit in Part Bclinically significant changes in laboratory evaluations
Secondary: 
to determine the PK of AQ280 after single and multiple oral dosesto determine the PK of the AQ280 main metabolite, AQ282, after single and multiple oral dosesto determine the effect of food on the PK of AQ280 after single oral dose	
Part A (SAD):
 
primary PK parameters derived from plasma concentration-time profile of AQ280: $AUC_{0-\infty}$, C_{max} ($AUC_{0-tlast}$ may be included as a primary PK parameter if $AUC_{0-\infty}$ cannot be calculated)primary PK parameters derived from plasma concentration-time profile of the AQ280 main metabolite, AQ282: $AUC_{0-\infty}$, C_{max} ($AUC_{0-tlast}$ may be included as a primary PK parameter if $AUC_{0-\infty}$ cannot be calculated)comparison of the primary PK parameters of AQ280 after single dose administration in the fasted state and in the fed state 
Part B (MAD):
 
primary PK parameters derived from plasma concentration-time profile of AQ280 on Day 1 and Day 7: AR, AUC_{τ}, C_{max}primary PK parameters derived from plasma concentration-time profile of the AQ280 main metabolite, AQ282, on Day 1 and Day 7: AUC_{τ}, C_{max}

Abbreviations: AR = accumulation ratio; AUC_{0-∞} = area under the concentration-time curve from time 0 extrapolated to infinity; AUC_{0-t_{last}} = area under the concentration-time curve from time 0 to the time of the last quantifiable concentration; AUC_T = area under the concentration-time curve over a dosing interval; CL/F = apparent total clearance; C_{max} = maximum observed concentration; CCI = electrocardiogram; CCI =

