7.1. Pharmacokinetic Assessments

7.1.1. Sample Collection and Processing

Blood samples will be collected by venipuncture or cannulation at the times indicated in the Schedules of Assessments in [Appendix 6](#). The DEC may decide to alter the sampling schedule, allowing for up to 3 additional samples to be taken and up to 2 additional outpatient visits if additional samples beyond 48 hours postdose (but within 7 days post final dose) are required. The maximum volume of blood withdrawn per subject will not exceed the limit detailed in [Appendix 3](#). Any changes to the scheduled times of PK assessments will be agreed with the sponsor and documented in the TMF. Samples taken from subjects who received placebo will be analyzed.

Procedures for collection, processing, and shipping of PK blood samples will be detailed in a separate document.

CC1

CCI

Procedures for collection, processing, and shipping of urine samples will be detailed in a separate document.

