8.3. Pharmacokinetic Analyses

Plasma concentrations of AQ280 and its main metabolite, AQ282, and plasma PK parameters will be listed and summarized by descriptive statistics per dose group and (for Part B only) day. Concentration-time profiles will be generated per dose group.

Pharmacokinetic parameters will be determined from plasma concentrations of AQ280 and its main metabolite, AQ282, using standard noncompartmental methods. Full details of PK parameters will be presented in the statistical analysis plan for this study.

In Part A, where data are available, AQ280 dose proportionality will be examined across groups. The PK parameters AUC from time 0 extrapolated to infinity ($AUC_{0-\infty}$), AUC from time 0 to the time of the last quantifiable concentration ($AUC_{0-t_{last}}$), and C_{max} , will be analyzed for dose proportionality using a power model approach or analysis of variance (ANOVA) model as appropriate. Where data are available, the effect of food at 1 dose level in Part A will be investigated using ANOVA.

In Part B, the PK parameters AUC over a dosing interval (AUC_{τ}) and C_{max} , on Day 7 will be analyzed for dose proportionality using a power model approach or ANOVA model as appropriate.

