Appendix 6: Schedule of Assessments

Schedule of Assessments – Part A (Single Ascending Dose)

Visit Name	Screening	Check-in	Treatment period			Follow-up ^a	Early termination (if applicable)	Comment (*)
Visit No.	1		2			3		
Day No. Visit window (calendar days)	-35 to -2	-1	1	2	3	8 (±2 days)		
Trial population and eligibility								
Informed consent*	X							The ICF must be signed prior to performing any protocol-related procedures, including, but not limited to, screening evaluations.
Subject eligibility	X	X						
Demographics	X							
Medical history	X							
Height and weight	X							
Alcohol breath test	X	X						
Urine drug screen	X	X						
Serology*	X							Hep B surface antigen, hep C virus antibody, HIV antibodies.
Quantiferon™ TB Gold test	X							
Serum pregnancy test*	X							All females.
FSH*	X							All females.
Trial residency								
Check-in		X						
Check-out					X			
Nonresidential visit	X							
Treatment and randomization								
Concomitant medication and concurrent procedures	X	X	X	X	X	X		
Randomization			X					
IMP administration*			X					Subjects will be dosed in a fasted state.
Safety assessments								
Physical examination*		X			X		X	Full physical examination performed at check-in. Symptom-directed physical examination at all other times.

Visit Name	Screening	Check-in	Treatment period			Follow-up ^a	Early termination (if applicable)	Comment (*)
Visit No.	1		2			3		
Day No. Visit window (calendar days)	-35 to -2	-1	1	2	3	8 (±2 days)		
Vital signs	X	X	X*	X*	X*		X	Day 1: Predose (triplicate), 1, 2, 4, 6, 8, and 12 hours postdose. Day 2: 24 hours postdose. Day 3: 48 hours postdose. Timepoints may be adjusted based on emerging data.
Safety ECG	X	X	X*	X*	X*		X	Day 1: Predose (triplicate), 2, 4, and 8 hours postdose. Day 2: 24 hours postdose. Day 3: 48 hours postdose.
Telemetry/continuous ECG*			X*	X*				See footnote b. Day 1: 3 readings predose (-60, -45, and -30 minutes), 0.25, 0.5, 1, 1.5, 2, 3, 4, 6, 8, and 12 hours postdose. Day 2: 24 hours postdose.
All hematology, coagulation, and clinical chemistry	X	X		X*	X*		X	Day 2: 24 hours postdose. Day 3: 48 hours postdose.
Urinalysis	X	X			X*		X	Day 3: 48 hours postdose.
Urine pregnancy test*		X			X		X	Only female subjects.
Adverse events	X		X			X	X	
PK/PD assessments								
PK blood sample*			X*	X*	X*		X	See footnote c. Day 1: Predose, 0.25, 0.5, 1, 1.5, 2, 3, 4, 6, 8, and 12 hours postdose. Day 2: 24 and 36 hours postdose. Day 3: 48 hours postdose.

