## 7.5. Pharmacokinetic Assessments

### 7.5.1. Pharmacokinetic Analysis

The following PK parameters will be determined where possible from the plasma concentrations of AQ280 and AQ282 using noncompartmental methods in validated software program Phoenix WinNonlin (Certara, Version 8.1.1 or higher):

Parameter	Units a	Definition
AUC 0-tlast	h*ng/mL	area under the concentration-time curve from time 0 to the time of the last quantifiable concentration (t last ) (Part A and Day 1 of Part B only) b
AUC 0-24	h*ng/mL	area under the concentration-time curve over the time interval 0 to 24 hours postdose b
AUC τ	h*ng/mL	area under the concentration-time curve over the dosing interval (Part B only) b
AUC 0-∞	h*ng/mL	area under the concentration-time curve from time 0 extrapolated to infinity c (Part A and Day 1 of Part B only)
%AUC extrap	h*ng/mL	percentage of area under the concentration-time curve due to extrapolation from the last quantifiable concentration to infinity (Part A and Day 1 of Part B only)
C max	ng/mL	maximum observed concentration
t max	h	time of the maximum observed concentration
t last	h	time of the last quantifiable concentration
C trough	ng/mL	concentration at the end of the dosing interval
t 1/2	h	apparent terminal elimination half-life
CL/F	L/h	apparent total clearance (AQ280 only)
V z /F	L	apparent volume of distribution during the terminal phase (AQ280 only)
MR AUC		metabolite:parent ratio based on AUC 0-∞
MR Cmax		metabolite:parent ratio based on C max
F rel, AUC0-∞		relative bioavailability in the fed and fasted state based upon AUC 0-∞ (Food effect group (A3) only)
F rel, Cmax		relative bioavailability in the fed and fasted state based upon C max (Food effect group (A3) only)
AR AUC		accumulation ratio based on AUC 0-τ (Part B only)
AR Cmax		accumulation ratio based on C max during the dosing interval (Part B only)
LR		Linearity ratio
DAUC 0-tlast	h*ng/mL/mg	AUC 0-tlast normalized by dose administered.
DAUC 0-24	h*ng/mL/mg	AUC 0-24 normalized by dose administered

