### 7.5.1.2. Criteria for Calculation and Reporting of Area Under the Concentration-time Curve

The minimum requirement for the calculation of AUC will be the inclusion of at least 3 consecutive concentrations above the lower limit of quantification. If there are only 3 consecutive concentrations, at least 1 should follow  $C_{max}$ . An exception may be made for metabolites, where  $C_{max}$  may be the last timepoint.

If the extrapolated area is  $> 20\%$ ,  $AUC_{0-\infty}$  (and derived parameters) may be excluded from the summary statistics and statistical analysis at the discretion of the sponsor or pharmacokineticist.

If  $AUC_{0-\infty}$  cannot be determined reliably for all subjects and/or dose levels, an alternative AUC measure, such as AUC to a fixed timepoint, may be used in the statistical analysis of dose proportionality/food effect.

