### **7.5.1.3. Criteria for Handling Concentration Below the Limit of Quantification or Missing Concentrations for Pharmacokinetic Analysis**

Plasma concentrations below the limit of quantification (BLQ) will be assigned a value of 0 before the first measurable concentration and thereafter BLQ concentrations will be treated as missing. The following rules apply to the specific situations defined below:

- If an entire concentration-time profile is BLQ, it will be excluded from PK analysis.
- Where 2 or more consecutive concentrations are BLQ at the end of a profile, the profile will be deemed to have terminated and any further quantifiable concentrations will be set to missing for the calculation of the PK parameters, unless they are considered to be a true characteristic of the profile of the drug.
- If a predose analyte concentration is missing, following a single dose (Part A) or Day 1 dose (Part B) it will be set to 0 by default within Phoenix WinNonlin.
- For multiple dose part of the study (Study Profile Day 7), if the analyte concentration at the end of the dosing interval ( $\tau$ ) is missing, this may be substituted with the predose concentration. Similarly, if the predose concentration is missing then this may be substituted with the concentration at  $\tau$ .

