### **7.5.3. Pharmacokinetic Statistical Methodology**

#### **7.5.3.1. Dose Proportionality**

A statistical analysis will be conducted to investigate the dose proportionality of  $AUC_{0-t_{last}}$ ,  $AUC_{0-\infty}$ , and  $C_{max}$  for AQ280 and AQ282 on profile day 1 for Part A and  $AUC_{0-t}$  and  $C_{max}$  for AQ280 and AQ282 on profile day 7 for Part B.

The PK parameters will be analyzed using a power model that will have the following form:

$$parameter = intercept \times dose^{slope} \times random\ error$$

Using the natural log (ln) transformation, a power model can be expressed as a linear regression equation:

$$\ln(parameter) = intercept + slope \times \ln(dose) + random\ error$$

Dose proportionality holds if the slope of the regression line is close to 1. The estimate of the slope and its 95% confidence interval will be used to quantify the degree of non-proportionality. For each PK parameter separately, a pooled estimate (across all doses) of slope, corresponding 95% confidence interval (CI), and between-subject coefficient of variation (CV) will be calculated. Figures (on the logarithmic-logarithmic scale) containing individual values, the power model line (95% CI), and the dose proportionality line (defined as the power model line with slope of 1) will be created for each PK parameter. Additionally, figures (on the logarithmic-linear scale) containing individual values and geometric means will be created for each corresponding PK parameter normalized by dose administered.

The lack of fit test will be conducted for the statistical assessment of linearity assumption, and thus appropriateness of a power model. The lack of fit model will be the same as the power model fitted, but with dose included as an additional fixed effect. The statistical

assessment will rule the linearity assumption acceptable if the diagnostic plots appear reasonable and the lack of fit 2-sided p-value  $>0.05$  (dose effect is not significant at the 0.05 level of significance). The assessment of linearity assumption may also occur via visual examination of the figures by the pharmacokineticist. This assessment may override the statistical assessment; where this occurs, it will be detailed in the CSR.

If the assumption of linearity is ruled acceptable and the 95% CI for the slope spans 1, it will be deemed that there is no statistical basis to conclude a lack of proportionality.

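### Part A tests dose proportionality on AUC0-tlast, among other parameters; its interval can lengthen with dose, so unless the assay limit is low, proportional PK can look supra-proportional on that parameter

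*SAP*

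**What the plan says.** SAP 7.5.3.1 begins "A statistical analysis will be conducted to investigate the dose proportionality of" and lists AUC0-tlast, AUC0-inf and Cmax for both analytes in Part A. A power model is fitted to each parameter separately. If linearity is accepted and the 95% CI for the slope covers 1, there is held to be no statistical basis for concluding a lack of proportionality. Protocol 8.3 also includes "AUC from time 0 to the time of the last quantifiable concentration", but names only AQ280 for Part A.

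SAP 7.5.1 defines AUC0-tlast as "area under the concentration-time curve from time 0 to the time of the last quantifiable concentration". Under SAP 7.5.1.3, values below the limit count as 0 before the first measurable concentration, and "thereafter BLQ concentrations will be treated as missing". The Part A sampling times (protocol Appendix 6) are "Predose, 0.25, 0.5, 1, 1.5, 2, 3, 4, 6, 8, and 12 hours postdose. Day 2: 24 and 36 hours postdose", then 48 h.

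Protocol Table 2 and SAP Table 1 name AUC0-inf and Cmax as the primary PK parameters for Part A. AUC0-tlast "may be included as a primary PK parameter if" AUC0-inf cannot be calculated. SAP 7.5.1.2 lets the sponsor or pharmacokineticist exclude AUC0-inf when more than 20% is extrapolated. If AUC0-inf is unreliable, an AUC to a fixed timepoint "may be used in the statistical analysis of dose proportionality/food effect". AUC0-24 is derived but is not on the proportionality list. Part B uses the dosing-interval AUC on Day 7.

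**The concern.** A slope tests proportionality fairly only if every dose is measured over the same interval, or over the whole curve. AUC0-tlast does neither. A low-dose profile falls below the assay limit earlier, loses more of its area and so tilts the fitted line upwards. The slope then mixes assay sensitivity with pharmacokinetics, yet SAP 7.5.3.1 reads it by the same rule as the other parameters and gives no warning.

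At stake is a misleading supra-proportional finding in support of the secondary PK objective, possibly beside a proportional AUC0-inf with no stated way to settle the conflict. The fallback wording makes this worse. Heavy truncation at low doses is what makes AUC0-inf unreliable, and the endpoint tables then point to the parameter that truncation biases.

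**Working it through.** The plan states no error rate or power for this analysis, so there is no figure to reproduce.

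**Inputs from the documents.** Predicted Cmax 35 ng/mL and AUC 303 ng/mL*h at 10 mg (protocol 3.5.1); first dose 3 mg; 5 groups with 6 active subjects each; the sampling times above; the slope rule with a 95% CI.

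**Assumptions.** One compartment with first-order absorption; doses 3/10/30/60/100 mg (only 3 mg is fixed, and capsule strengths run from 3 to 100 mg); CV 30%; LLOQ 0.05 to 2 ng/mL (protocol 7.1.2 leaves assay details to a separate document).

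**1. Typical profile.** AUC/Cmax = 303/35 = 8.66 h, which allows a half-life of at most about 6 h. Take 5 h:
- k = ln 2/5 = 0.1386 per h.
- Dose/V at 10 mg = 303 × 0.1386 = 42.0 ng/mL.
- Cmax of 35 then requires ka = 2.26 per h, and ka/(ka − k) = 1.065.

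The late concentration is (dose/10) × 42.0 × 1.065 × exp(−kt):
- 3 mg: 2.54 at 12 h, 0.48 at 24 h.
- 100 mg: 3.04 at 36 h, 0.58 at 48 h.

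**2. Area lost** = [C(tlast)/k]/AUC.
- LLOQ 1, 3 mg: tlast 12 h, (2.54/0.1386)/90.9 = 20.2%.
- LLOQ 1, 100 mg: tlast 36 h, (3.04/0.1386)/3030 = 0.7%.
- Slope from these two doses: 1 + ln(0.993/0.798)/ln(100/3) = 1 + 0.219/3.507 = 1.06.
- LLOQ 0.2: 3.8% lost at 3 mg (tlast 24 h) and 0.1% at 100 mg (tlast 48 h), so the slope is 1 + ln(0.999/0.962)/3.507 = 1.01.

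**3. Precision of the slope.** The sum of squares of ln(dose) over 30 subjects is 47.9. The log-scale SD is √ln(1 + 0.30²) = 0.294. So SE = 0.294/√47.9 = 0.0424, and the CI half-width is 2.048 × 0.0424 = 0.087.

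**4. False-finding rate.** The calculated rate uses a non-central t with 28 df and non-centrality (slope − 1)/SE. The simulated rates are for exactly proportional PK (half-life 4 to 5.5 h, 10% residual error, linear-up/log-down).

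| LLOQ (ng/mL) | Mean simulated slope | (slope − 1)/SE | Calculated | Simulated |
|---|---|---|---|---|
| 0.2 | 1.009–1.011 | 0.21–0.26 | about 6% | 3–7% |
| 0.5 | 1.027–1.029 | 0.64–0.68 | 9–10% | 7–11% |
| 1 | 1.045–1.053 | 1.06–1.25 | 18–23% | 15–23% |
| 2 | 1.067–1.081 | 1.58–1.91 | 33–45% | 30–44% |

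From LLOQ 0.5 upwards nearly all false findings are supra-proportional. AUC0-inf, and AUC0-24 extrapolated where tlast falls short of 24 h, gave mean slopes of 0.994 to 1.000 and rates of 2 to 6%.

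**5. Sensitivity** (LLOQ 1, half-life 5 h).
- The rate is 39% at CV 20%, 23% at CV 30% and 10% at CV 50%.
- Dose ranges of 3–60 mg and 3–200 mg give 17% and 19%.
- Across all settings the lack-of-fit test rejected in only 3 to 11% of trials, so it gives little protection.

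**6. Where AUC0-inf may drop out.** The share of 3 mg parent profiles with more than 20% extrapolated is about 5 to 7% at LLOQ 0.5, 31 to 32% at 1 and 71 to 76% at 2.

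**7. A lower-concentration analyte.** With the same profile shape, an analyte at fraction f of the parent behaves like the parent at LLOQ/f. At f = 0.5, LLOQ 1 acts like 2 (30 to 44%). At f = 0.2, LLOQ 0.1 acts like 0.5 (about 11%), and LLOQ 0.5 and 1 gave 48 to 56% and 94 to 96% in simulation. The documents give no level for AQ282.

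**The case against.** The strongest reply is that AUC0-tlast does not carry the conclusion. AUC0-inf and Cmax are the named primary parameters and are tested separately. In the simulated setting AUC0-inf met the SAP's criteria of at least 3 points and adjusted R² of at least 0.7 in essentially every parent profile, and its CI kept its error rate. If it fails, SAP 7.5.1.2 already permits a fixed-timepoint AUC. tlast and %AUCextrap are summarised by treatment, so unequal intervals would be visible. The SAP urges caution and uses the slope to quantify departure from proportionality; it does not declare an automatic failure. The size also rests on an unseen LLOQ, and with a sensitive assay there is no problem.

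Most of this stands, and it bounds the point. It does not remove it. The same interval rule is applied to AUC0-tlast without qualification, the discretion to exclude AUC0-inf bites on the truncated low-dose profiles, and two fallbacks coexist with no rule for choosing between them.

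A reader might also infer that the sampling flexibility in protocol 7.1.1, "allowing for up to 3 additional samples to be taken" with visits beyond 48 h if needed, adds materially to the bias. It does not in this setting: 48 h is nearly 10 half-lives at 5 h, and the mean simulated area lost at 100 mg with LLOQ 1 was 1.0%.

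**Conclusion.** The point holds for AUC0-tlast in Part A, conditionally on the assay. If the LLOQ is not low relative to the 3 mg profile, or to the AQ282 profile, proportional PK can be reported as supra-proportional on that parameter. The parent's false-finding rate runs from nominal at LLOQ 0.1 to 0.2 ng/mL to 30 to 44% at 2. These rates rest on the assumed PK model, dose range, CV and LLOQ.

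A reader might infer that the whole dose-proportionality assessment is unsound. The documents do not support that: AUC0-inf and Cmax are analysed alongside, and Part B uses a dosing-interval AUC. Nor do they support calling AQ282 the worse case or quoting the highest rates as expected, because its concentrations are not given.

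What remains is a gap in the fallback rule: the truncation-biased measure may become primary, while the unbiased one is optional.

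**What to change.** - In SAP 7.5.3.1, let AUC0-inf and Cmax carry the Part A conclusion, and make AUC0-tlast descriptive only. Align protocol 8.3.
- In SAP 7.5.1.2, SAP Table 1 and protocol Table 2, name a common-interval AUC as the single pre-specified fallback for both analytes when AUC0-inf is excluded or not estimable.
- Use the already derived AUC0-24. If 24 h is not quantifiable at the lowest dose, use the latest nominal time quantifiable in all dose groups. Fix the rule for this choice in advance, including how a single early-terminating profile is treated, so that the interval is not picked after the slopes are seen.
- Show tlast and %AUCextrap by dose beside each slope.

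The cost is wording and at most one extra partial AUC per analyte. The downside is that a shorter common interval covers less of the total exposure and is less sensitive to late, dose-dependent elimination; AUC0-inf still addresses that where it is estimable. The sponsor can judge the urgency by comparing its LLOQ with the predicted 3 mg concentrations at 12 and 24 h.

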**Table 3: Presentation of Study Treatment Sequences in TFLs (Part A; Food-effect Group Only)**

Group	Study Treatment Sequence	Order in TFLs
A3	Placebo (Fasted) / Placebo (Fed)	1
	XX mg AQ280 (Fasted) / XX mg AQ280 (Fed)	2

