**Table 4: Presentation of Study Treatments in TFLs (Part B)**

Group	Study Treatment	Order in TFLs
B1 to B3	Placebo	1
B1	XX mg AQ280 QD	2
B2	XX mg AQ280 QD	3
B3	XX mg AQ280 QD	4

QD = once daily

All TFLs will be based on actual treatments (eg, if subject was assigned to receive placebo but was wrongfully dosed with active treatment they would be summarized and listed under active treatment).

The TFLs will reflect the dose levels utilized in the study, and these will be displayed in increasing order.

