### **7.5.1.4. Treatment of Outliers in Pharmacokinetic Analysis**

If a value is considered to be anomalous due to being inconsistent with the expected PK profile, it may be appropriate to exclude the value from the PK analysis. However, the exclusion of any data must have strong justification and will be documented in the CSR.

Any quantifiable predose concentration value in the first treatment period will be considered anomalous and set to missing for the PK analysis. This will be set to 0 by default in Phoenix WinNonlin.

If the predose concentration is  $>5\%$  of  $C_{max}$  in the second treatment period for the food effect group (A3), all PK concentration and parameter data will be excluded from the summary statistics and statistical analysis for that period.

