### **Power Model Analysis**

```
proc mixed data = <data in> alpha = 0.05;
  by parcat1n parcat1 pkday paramn param;
  model lpk = ldose / cl residual ddfm = kr2;
  ods output solutionf = <data out>;
run;
```

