#### 7.5.3.2. Food Effect

A statistical analysis will be conducted to investigate the food effect on the treatment by comparing XX mg AQ280 (fed) treatment to XX mg AQ280 (fasted) treatment for Part A only.

The natural log (ln)-transformed AUC0-tlast, AUCt1-t2, AUC0-∞, and Cmax for AQ280 and AQ282 on profile day 1 will be analyzed using a mixed model. The model will include actual treatment as a fixed effect and subject as a random effect.

For each PK parameter separately, the least squares mean (LSM) for each treatment, difference in LSMSs between the fed and fasted treatments, and corresponding 90% and 95% confidence intervals (CIs) will be calculated; these values will then be back-transformed to give the geometric least square mean (GLSM), ratio of GLSMs, and corresponding 90% and 95% CIs; 2-sided p-value will also be calculated.

Additionally, the pooled estimate (across treatments) of the within-subject coefficient of variation (CV) will be calculated, and residual plots will be produced to assess the adequacy of the model(s) fitted.

Examples of the SAS code that will be used are as follows:

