#### Mixed Model Analysis

```
proc mixed data = <data in>;
  by parcat1n parcat1 pkday paramn param;
  class trtan usubjid;
  model lpk = trtan / cl residual ddfm = kr2;
  lsmeans trtan / cl pdiff = control('1') alpha = 0.1;
  lsmeans trtan / cl pdiff = control('1') alpha = 0.05;
  random intercept / subject = usubjid;
  ods output lsmeans = <data out>;
  ods output diffss = <data out>;
  ods output covparms = <data out>;
run;
```

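### Could the fed A3 profiles enter the Part A dose-proportionality analysis, and does the single placebo row in SAP Table 2 distort the comparator?

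*SAP*

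**What the plan says.** **Dose proportionality.** SAP 7.5.3.1 analyses the Part A parameters "for AQ280 and AQ282 on profile day 1 for Part A". The example power-model statement is "model lpk = ldose / cl residual ddfm = kr2". Its BY variables include the PK day but neither period nor treatment. If the lack-of-fit p-value is 0.05 or below, linearity is in principle rejected and the analysis moves to an ANOVA of the dose-normalised parameter. The pharmacokineticist may also judge linearity from the figures: "This assessment may override the statistical assessment".

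**Food effect.** SAP 7.5.3.2 handles this separately. The parameters "for AQ280 and AQ282 on profile day 1 will be analyzed using a mixed model", and the example code has the line "random intercept / subject = usubjid".

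**Exclusion of Period 2 data.** SAP 7.5.1.4 provides that, when the predose concentration exceeds 5% of Cmax "in the second treatment period for the food effect group (A3), all PK concentration and parameter data will be excluded" from summaries and statistical analysis.

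**Placebo.** SAP Table 2 has one placebo row covering A1 to A5, while A3 active treatment has a fasted and a fed row. Table 3 separates fasted from fed placebo, but only as parts of a sequence. Below Table 4 the SAP adds: "All TFLs will be based on actual treatments". SAP 7.1.5 re-baselines the food-effect group in each period.

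**The concern.** The day label does not separate fasted from fed, because both A3 profiles fall on day 1 of their period. The 5% carryover rule removes only contaminated Period 2 profiles, so a clean fed profile is not excluded by any stated rule. Protocol 8.3 says only that proportionality is examined across groups.

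If the fed profiles entered, six subjects would be counted twice as if independent, and any food effect would sit at a single dose. It would look like curvature. A drug with proportional PK could then fail the lack-of-fit test and be sent to unadjusted pairwise comparisons, and the CV labelled between-subject would also carry food and within-subject variation.

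The placebo row raises a smaller issue. The two A3 placebo subjects are dosed twice and appear in one column. An A3 active subject with the same preferred term in both periods is counted once in each of two columns; an A3 placebo subject is counted once. Safety is the primary objective, and this column is its comparator.

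**Working it through.** **1. Counts.** The plan's own figure is reproduced: 8 × 5 = 40 subjects in Part A. With 6:2 allocation this gives 6 × 5 = 30 active and 2 × 5 = 10 placebo subjects.

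| Data used | Profiles | Subjects | Slope df | Lack-of-fit df |
|---|---|---|---|---|
| Fasted only | 30 | 30 | 28 | 3 and 25 |
| With A3 fed | 36 | 30 | 34 | 3 and 31 |

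The placebo column would hold 10 + 2 = 12 dosing occasions from 10 subjects.

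**2. What inclusion by mistake would cost.** The documents give no food effect, no variability and no doses after 3 mg, so these are assumptions: exactly proportional PK, nine illustrative dose ladders, six active subjects per dose, total CV 30–60%, within-subject CV 15–25%. There were 20,000 simulated trials per scenario.

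| Fed/fasted ratio | False lack-of-fit rate |
|---|---|
| Fasted only | 5% |
| 1.0 | 7–9% |
| 1.25 | 10–15% |
| 1.5 | 14–27% |
| 2.0 or 0.5 | 22–51% |
| 3.0 | 37–79% |

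The chance of the correct conclusion (linearity accepted and the slope CI spanning 1) is 90–91% with fasted data. With fed profiles it is about 85–88% at ratio 1.0, 81–85% at 1.25 and 48–74% at 2.0. At ratio 2.0 the slope CI still covers 1 in 94–99% of trials.

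**3. Direct check of slope and CV** (ladder 3/10/30/60/100 mg, ratio 2.0).

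- Slope: with 6, 6, 12, 6 and 6 profiles, mean ln(dose) = 3.1505 and Sxx = 48.37. Bias = 6 × (ln 30 − 3.1505) × ln 2 / Sxx = 6 × 0.2507 × 0.6931 / 48.37 = 0.022. Simulation gave 0.021. It is small because the third of five doses lies near the centre of the ln(dose) range.
- CV: take between-subject CV 25% and within-subject CV 20%. The variances are ln(1.0625) = 0.0606 and ln(1.04) = 0.0392, total 0.0998, so CV = √(exp(0.0998) − 1) = 32%. With fed profiles the expected within-dose sum of squares is 20 × 0.0998 = 1.997 at the other four doses, 12 × 0.0998 − 2 × 0.0606 − 0.0392 = 1.038 at the third dose, plus 12 × (ln 2 / 2)² = 1.441 for food. The sum, 4.476, divided by 31 is 0.1444, so CV = 39%. Simulation gave a median of 39%.

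**4. Would an analyst include them?** The text points the other way:

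- Protocol 8.3 and SAP 7.5.3 separate proportionality (across groups) from food (one dose level).
- SAP 3.1.1 has every group dosed fasted on Day 1, including Period 1 of A3. Fed dosing occurs only in A3 Period 2.
- Table 2 gives A3 fasted and A3 fed separate treatment rows.
- The power model reports a between-subject CV and has no subject effect. Where subjects repeat, in 7.5.3.2, the same SAP adds one. That contrast implies one profile per subject in 7.5.3.1.
- The code is an example run on a placeholder dataset, so missing BY variables say nothing about how that dataset is selected.

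**5. Placebo incidence.** Let p be the per-period probability of an event and ρ the within-subject correlation. Incidence = [8p + 2(1 − (1 − p)² − ρp(1 − p))] / 10.

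| p | ρ = 0 | ρ = 0.5 | ρ = 1 |
|---|---|---|---|
| 0.1 | 0.118 | 0.109 | 0.100 |
| 0.2 | 0.232 | 0.216 | 0.200 |
| 0.3 | 0.342 | 0.321 | 0.300 |
| 0.5 | 0.550 | 0.525 | 0.500 |

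The largest rise is 0.018 to 0.050, about 0.2 to 0.5 of one subject in 10.

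**The case for a change.** The best argument for a change is that intent is not specification. The SAP supersedes the protocol's statistical text, no sentence in either document limits 7.5.3.1 to fasted data, and the TFL shells, which might, are not available here. An open choice of dataset could in theory be settled after the food effect is known. The override is discretionary, and the remedy is a single sentence.

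It is true that the restriction is unwritten and that the lack-of-fit test would suffer if it were ignored. That does not make it a defect in the analysis. The larger error rates need three things together: fed profiles actually included, a sizeable food effect, and nobody intervening. The third is unlikely, because 7.5.3.1 also requires reasonable diagnostic plots and shows individual values against the fitted line. Twelve points at one dose, six of them shifted, would stand out among groups of six. SAP 7.1 already urges caution because the sample size is not based on power.

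On placebo, the asymmetry in counting is real, but pooling of both periods is inferred from a row label and not stated. Counting a subject once per preferred term within a treatment is ordinary incidence counting.

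**Conclusion.** No change follows. For dose proportionality this is missing detail that the rest of the plan fills: the evident dataset is the 30 fasted profiles, with A3 contributing Period 1. Stating this in 7.5.3.1 would be a harmless clarification, but the planned analysis would stay the same. The rise in false lack-of-fit from 5% to 7–9% (no food effect) or 22–51% (twofold effect) measures a programming mistake that the plan does not prescribe, under assumed doses, variability and food ratio. Even then the slope bias at a twofold effect is at most 0.05. The question disappears if the sponsor does not run the fed period, which Protocol Appendix 6 leaves open.

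The placebo row is a presentation trade-off. Its effect is at most half a subject in 10, in tables for which SAP 7.7.6 plans no inferential analysis. Placebo subjects are outside the PK population, so no PK result is touched. A separate fed placebo column would have n = 2 and, under SAP 7.1.2, show only n, minimum and maximum for continuous data. Limiting the column to Period 1 would leave the fed active column without a placebo comparator in the summaries. Neither layout is clearly better than the one planned.
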